Data analysis: Aim 1 data analysis will entail thematic analysis of semi-structured interviews supplemented by application of narrative inquiry techniques. The qualitative descriptive analysis will involve iterative coding, memoing, winnowing, and consensus-development around themes by analytic teams at each site and then across sites, led by the qualitative Co-I [name]. Narrative inquiry of responses will address personal accounts elicited from women about encounters while trying to get tested or getting a vaccine, or stories about what peers and media are saying about testing and vaccines in their communities. Story-based interviewing allows for interpretation of meaning along formal and performative indices in addition to the more standard focus on repeated themes. We have used the narrative analytical approach in previous research and found that, with its extended units of analysis, the story-based technique renders visible nuances of perspective and experience that may be obscured in other qualitative methods (refs 47,48). For Aim 2, a descriptive analysis of survey items on acceptability and usability will be conducted and guide subsequent changes for interventions. Qualitative data will be analyzed using a thematic analysis across interviews and will be led by MPIs [name] (health communications/mHealth intervention expert) and [name] (jail health literacy intervention expert) to decide how and where to make changes in the final mHealth intervention. Aim 3 data analysis will include a series of quantitative assessments led by Co-I [name]. First, bivariate tests will be performed to examine the distributional properties of the survey data (COVID-19 test completion, testing and vaccine literacy, access, and uptake), website log data (usage of and interaction with the COVID-19 literacy module; i.e., intervention fidelity/dosage), and their correlations at each time point (0, 1, 12 months) within the sample, as well as in comparisons between participant subgroups (study sites, age, race/ethnicity, education, employment, etc.). Second, growth curve modeling (GCM) will be utilized to explore the changes in each outcome over the 13-month study period, while properly accounting for (a) the dependency of observations (e.g., autoregressive residual covariance), (b) the baseline characteristics imbalanced between dropouts and completers, and (c) other confounders (e.g., study sites reflecting policy climate/local promotion of testing and vaccine, age, race/ethnicity, education, intervention fidelity/dosage). Third, hierarchical linear modeling (HLM) will be conducted to estimate the longitudinal impacts of COVID-19 literacy, attitudes, mistrust, hesitancy (independent variables) on test completion, vaccine access, and uptake

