Power considerations: Aim 1 will have 60 participants total, that is 20 from each site. The goal for Aim 1 is not thematic saturation, but rather to collect enough information from stakeholders to supplement what is known in the health literacy and COVID-19 communication literature to develop the intervention.³⁹ Given on our prior research in developing health literacy interventions based on stakeholder interviews³⁰⁻³¹, 60 participants will be sufficient to meet our goals. If we feel that we don't have enough information to detect regional differences in stakeholders' feedback and believe that some may exist, we have the time and resources to ask more structured questions in this regard. Aim 2 will be piloted with 45 participants, 15 from each site. The goal of the pilot is to work out kinks in the mHealth intervention delivery, multimedia design, see which parts of the intervention are great, and which ones don't resonate, and to get feedback on what other areas of content need to be added in. In our prior research developing health literacy interventions²⁷, this sample is sufficient. We expect a complete sample of 313 participants for Aim 3 based on a 95% acceptance rate and 81% completion rate over the 13-month study period. Because there is little or no previous research that can guide power calculation for our Aim 3 investigation, we estimated minimum detectable effect size (MDES).⁴⁰ This approach provides an insight for the smallest 'true' effect for which this study can detect with $N=313$, 80% power, and Type I error controlled under 5%. The estimated MDES are small— $d=0.15$ for mean difference, $g=0.08$ for proportion difference, $\rho=0.16$ for correlation, and $f=0.08$ for GCM/HLM when 0.30 correlation is reasonably assumed among repeated measurements. These results suggest that this study will be adequately powered (> 80%) even when the 'true' effects of the intervention are small in this population.

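### The only covariance structure named for the growth curve model, an autoregressive residual, suits waves at 0, 1 and 12 months poorly and does not by itself match the 0.30 correlation used for power

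*Combined protocol and SAP*

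**What the plan says.** All references are to the APPROACH part of the combined protocol and SAP.

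- **Data analysis, Aim 3, waves.** Survey and website-log data are to be examined along with "their correlations at each time point (0, 1, 12 months) within the sample". The gaps are therefore 1 month and 11 months.
- **Data analysis, Aim 3, model.** The plan states that "growth curve modeling (GCM) will be utilized to explore the changes in each outcome over the 13-month study period". Among the things the model is to account for is "the dependency of observations (e.g., autoregressive residual covariance"). The order of the autoregression, whether it runs on wave number or calendar time, whether random effects are included, and whether standard errors are robust are all left open.
- **Power considerations.** The plan states "We expect a complete sample of 313 participants for Aim 3", with "80% power, and Type I error controlled under 5"%. The minimum detectable effect size (MDES) is f = 0.08 "for GCM/HLM when 0.30 correlation is reasonably assumed among repeated measurements". One correlation is given, with no statement of how it depends on the gap between waves.

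**The concern.** An autoregressive structure ties the correlation between two waves to the distance between them. In its usual equal-step form, AR(1) on wave number, it treats the 1-month and 11-month gaps as the same distance. It forces the 0–1 and 1–12 correlations to be equal and makes the 0–12 correlation the square of that common value. In continuous time, a moderate 1-month correlation drives the 11- and 12-month correlations almost to zero. Neither form, used alone, yields 0.30 for every pair.

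The study has no control group, so within-woman change is the evidence of effect, and its standard error depends directly on the correlation between the two waves compared. A poor covariance model can make one contrast look less certain than it is and another more certain. The 1-to-12-month contrast is the one that shows whether an early gain lasts.

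**Working it through.** **Inputs from the plan.** Waves at 0, 1 and 12 months; N = 313; 80% power; 5% type I error (taken as two-sided, since the plan does not say); correlation 0.30; stated MDES f = 0.08.

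**Assumptions of this check.** Continuous outcome, equal variances across waves (1 SD), complete data, wave means compared directly. The true correlation matrices are assumed, because the plan gives no estimates. Each working structure is fitted to the assumed true correlation matrix S by minimising log|R| + tr(R⁻¹S).

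**Step 1: the plan's own figure.** For a repeated-measures F test with m = 3 waves and exchangeable correlation r:

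λ = f²·N·m/(1 − r), df₁ = m − 1 = 2, df₂ = (N − 1)(m − 1) = 624.

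With N = 313 and r = 0.30, 80% power needs f = 0.08495, which rounds to the stated 0.08. A 1-df time contrast gives 0.0766, which also rounds to 0.08. The stated figure is thus reproduced with 0.30 read as common to all pairs.

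**Step 2: formula for the error.** The variance of a change between two waves is 2(1 − r)/N in SD² units. With equal variances, the ratio of model-based to true standard error is

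√[(1 − r_model)/(1 − r_true)].

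**Step 3: truth is 0.30 for every pair; autoregressive residual alone.**

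- Equal-step: the fit gives 0.30 (0–1), 0.30 (1–12) and 0.30² = 0.09 (0–12). The 0–12 ratio is √(0.91/0.70) = 1.140. In SD units the model reports √(2 × 0.91/313) = 0.0763 against a true √(2 × 0.70/313) = 0.0669.
- Continuous-time: the fit gives 0.30 (0–1) and practically 0 for the other two. The 0–12 and 1–12 ratios are √(1/0.70) = 1.195; the model standard error is 0.0799.

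**Step 4: illustrative truth of 0.6 (0–1), 0.3 (1–12), 0.3 (0–12).** Ratios of model-based to true standard error:

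| Working structure | Fitted correlations (0–1, 1–12, 0–12) | 0–1 | 1–12 | 0–12 |
|---|---|---|---|---|
| Equal-step AR alone | 0.45, 0.45, 0.2025 | √(0.55/0.40) = 1.17 | √(0.55/0.70) = 0.89 | √(0.7975/0.70) = 1.07 |
| Random intercept + equal-step AR | 0.45, 0.45, 0.30 | 1.17 | 0.89 | 1.00 |
| Random intercept + continuous-time AR | 0.60, 0.30, 0.30 | 1.00 | 1.00 | 1.00 |
| Compound symmetry | 0.40, 0.40, 0.40 | √(0.60/0.40) = 1.22 | √(0.60/0.70) = 0.93 | √(0.60/0.70) = 0.93 |

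A random intercept frees the 0–12 correlation, but with equal-step coding the 0–1 and 1–12 correlations remain forced to be equal, so those two errors stay.

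**Step 5: the direction is not fixed.** If the truth were continuous-time decay with a 12-month correlation of 0.30, the 0–12 ratio would be 0.94 for equal-step AR, 0.835 for compound symmetry and 1.00 for continuous-time AR.

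**Step 6: consequence for planning.** The detectable 0-to-12 change is (1.960 + 0.842) × √(2(1 − r)/313). That is 0.187 SD at r = 0.30, 0.214 SD at r = 0.09 and 0.224 SD at r near 0.

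**The case against.** A reader might infer that the plan contradicts itself and that its standard errors for the 12-month change are wrong. The documents support neither, for four reasons.

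1. The autoregressive form is introduced as an example, so the plan does not commit to it.
2. It is a residual structure inside a growth curve model. Such models usually carry woman-level random effects. If the truth is 0.30 for every pair, a random intercept plus an autoregressive residual, on either time scale, gives a ratio of 1.00 for every contrast. That combination is compatible with a common 0.30, so the two sections can both hold.
3. The 0.30 is a single planning value. The plan does not call it constant, and it does not bind the analysis.
4. The 14% and 20% errors are conservative, the 11% understatement rests on correlations that the plan does not give, and the plan designates no 0-to-12 contrast.

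All four stand as limits on the claim. They do not remove it. The protection in the second reason depends on choices that the plan does not make, and under equal-step coding a random intercept leaves the 0–1 and 1–12 errors in place.

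It can also be said that robust standard errors would repair an autoregressive model as well as any other, so the example need not be deleted. That is true of large-sample validity. Unstructured covariance is preferable because it needs no spacing assumption and costs almost nothing here.

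**Conclusion.** The point holds as a weakness of specification, and the change is an optional improvement. The only structure named is poorly suited to waves at 0, 1 and 12 months and does not by itself match the correlation behind the MDES.

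Used alone for continuous outcomes, it could make the model-based 0–12 standard error 14% to 20% too large if every pair correlates 0.30. Under the illustrative 0.6/0.3/0.3 pattern with equal-step coding, it could make the 0–1 standard error 17% too large and the 1–12 standard error 11% too small, with or without a random intercept.

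These sizes assume equal variances, complete data and model-based standard errors. They do not carry over directly to the yes/no outcomes. Size and direction both depend on the true correlations, which are unknown, and on modelling choices not yet stated. The check does not show that the trial's 12-month standard errors will be wrong, nor that the Data analysis and Power considerations sections conflict.

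**What to change.** In Data analysis (Aim 3):

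- For continuous outcomes, replace the autoregressive example with an unstructured within-woman covariance over the three waves.
- State whether time enters as actual months or as categorical waves.
- Use robust (sandwich) standard errors. If a simpler structure such as compound symmetry is kept as a fallback for non-convergence, they must accompany it: Step 4 shows that compound symmetry can itself overstate one standard error by 22% and understate others by 7%.
- For yes/no outcomes, name the equivalent GEE or mixed logistic model, with robust standard errors.

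In Power considerations, it would help to show the MDES over a range of 0-to-12 correlations as well as at 0.30.

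The cost is a few sentences and no new data. An unstructured covariance for three waves has six parameters against two for AR(1), so four more, with about 313 women expected to complete. It contains the compound-symmetry and autoregressive forms as special cases, and settling it now removes a choice that would otherwise be made after the data are seen.

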Sampling, recruitment: We will use convenience sampling for this study – in that we will recruit from the TriCity cohort (ref). Based on our prior experience, we expect 95% of women to accept participation in the new study. The sample currently available includes 108 women in Kansas City, 166 women in Birmingham, and 234 women in Oakland (ref). The Kansas City sample was originally recruited in jails (seven years ago) but has now been community based since (with some periodic local reincarceration). The Birmingham sample was recruited two years ago in a community corrections program. The Oakland sample was recruited through probation offices and in working with local reentry organizations, four years ago. We have maintained contact and excellent retention rates one and two years later across sites – at 82%.

For recruitment, women will be invited to participate by study staff at the respective sites, with an IRB-approved verbal consent that reviews study procedures, risks, benefits, and the voluntary nature of participation. For the last year, given the pandemic, 100% of research activities occurred virtually, with 95% of interviews over the phone and 5% over email or postal service mail correspondence. Though our study field sites are opening up, we expect most recruitment will be over the phone. At the end of the verbal recruitment and consent process, the study staff member will ask the woman, “Would you like to participate in this study?” We used this exact same method to recruit women into the original tri-city cohort study, since those women were already participating in other studies at each site. The method was IRB-approved, effective, and resulting in 95% participation among all of those invited (ref). An advantage is that the study team, particularly the field staff, has remained the same over the last seven-10 years. For the present study, participants will know the person inviting them, thus having the benefit of familiarity with personnel and typical study procedures. For sustainability purposes, we will work with stakeholders in Aims 1 and 3 to better understand how to reach new potential participants in future dissemination activities.

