We will tell women during the consent process that for Aim 1, 60 women will be randomly chosen to participate in interviews; and for Aim 2, that 45 women will be randomly chosen to provide feedback on an early stage of the intervention, but for Aim 3, that all women will be invited to participate. We will use a random number generator to select participants for Aim 1 and 2. If women complain during the consent process about unfairness and not being able to be selected for Aim 1 and 2 (which has not happened to us in the past), we will invite them to participate. Aim 1 and 2 do not mandate a random selection process for scientific reasons.

Attrition and retention: For Aim 1 and Aim 2, we will keep recruiting until we reach our desired sample size. Because Aim 1 and Aim 2 only have one time point of participation, attrition is not an issue. For Aim 3, we expect 95% of the 508 women to agree to participate in study, resulting in a sample of 483 women at baseline assessment for this aim. Based on our ongoing community-based mHealth women's health literacy RCT, where 81% of women who initiated the mHealth intervention completed it, we expect 391 to complete the intervention. Also based on our RCT, we are at 100% retention for the post-intervention follow-up, so we expect to retain all 391 women for the 1-month post-intervention follow-up. At the 12-month follow-up, we expect a final conservative attrition rate of 20%, based on our prior research activities following cohorts of women with community-based CLSI. Thus, the smallest expected N for the final sample will be 313 women.

Similarly, Aim 1 and Aim 2 should do not have retention issues, since activities occur at one point in time. For Aim 3, retention of participants for the post-intervention follow-ups will be accomplished through methods that our research teams have been using successfully for the last 10-20 years in our respective cities to achieve excellent follow-up rates with hard-to-reach samples, e.g. those with recent CLSI, drug users, and the homeless (refs tri city 68,69). These methods include supplementing existing participant contact information with names, addresses, phone numbers of participant, family members, friends; places of hanging out like bars, bodegas, street corners, or churches; places for usual drug or mental health treatment (with signed approval to contact these facilities), places of previous incarcerations, Facebook and Instagram handles. We

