
(challenges/barriers/facilitators, update [yes/no]; dependent variables). Site-specific effects will be identified in a follow-up subgroup analysis using data from the Kansas City, Birmingham, and Oakland subsamples. Lastly, a survival analysis will be conducted. Specifically, we will estimate the cumulative probability of taking COVID-19 test or vaccine over 12 months (i.e., survival function); and we fit Cox proportional hazards models to identify the factors (e.g., literacy, and demographic variables) that significantly contribute to the time to get vaccinated (i.e., survival time).

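### Site-specific effects are to be identified from separate city subsamples, with no interaction test or other criterion; at the plan's own minimum detectable effect such results cannot show whether effects differ by city.

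*Combined protocol and SAP*

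**What the plan says.** The Data analysis section of the combined protocol and SAP sets out the Aim 3 analyses in sequence: bivariate tests, growth curve modelling (GCM) of each outcome, hierarchical linear modelling (HLM) of literacy, attitudes, mistrust and hesitancy on testing and vaccine outcomes, and survival analysis. Directly after the HLM step it says: "Site-specific effects will be identified in a follow-up subgroup analysis using data from the Kansas City, Birmingham, and Oakland subsamples".

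Site appears in two other places in that section:

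- In the bivariate step, the survey and log data at each time point are examined "as well as in comparisons between participant subgroups (study sites, age, race/ethnicity, education, employment, etc".).
- In the GCM, site is one of the confounders to be adjusted for: "study sites reflecting policy climate/local promotion of testing and vaccine".

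The first compares levels at a time point. The second adjusts for site. Neither tests whether a change over time, or a predictor's association with an outcome, differs between cities.

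The Sampling, recruitment section gives the cohort by city: "108 women in Kansas City, 166 women in Birmingham, and 234 women in Oakland". The Attrition and retention section gives only pooled expectations, ending with "the smallest expected N for the final sample will be 313 women". The Power considerations section gives minimum detectable effects for the pooled 313 and none by city.

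**The concern.** A significant result in one city and a non-significant one in another is not evidence that the two cities differ. Each subsample result answers whether there is an effect in that city. Whether effects differ between cities needs a direct comparison, and none is planned.

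The Significance section lists variation in testing and vaccine beliefs by geographic region among the unknowns, and reports an anecdotal impression that Oakland women are more willing to be vaccinated. Readers will therefore look for city contrasts in the Aim 3 results. If three separate analyses are all they have, a chance pattern of significance may be taken for a regional difference and carried into the dissemination planning that is also part of Aim 3.

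**Working it through.** **Inputs from the plan.** Cohort 108 / 166 / 234 (total 508); 95% acceptance; 81% completion; 20% attrition at 12 months; pooled N=313; 80% power; 5% type I error; d=0.15 for a mean difference, with g=0.08, rho=0.16 and f=0.08 for the other measures.

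**Assumptions.** Loss is proportional to cohort size in each city. Tests are two-sided at 5% without adjustment (the plan does not state sidedness). d is the standardised within-woman change.

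**The plan's own figure.** MDES = (1.960 + 0.842)/√313 = 0.158 two-sided and 0.141 one-sided, against the stated 0.15. Two-sided power at d=0.15 is 75%. The stated figure is thus not reproduced exactly, but the result below hardly depends on it.

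**City sizes.** 313 × 108/508 = 66.5; 313 × 166/508 = 102.3; 313 × 234/508 = 144.2. This gives about 67 / 102 / 144.

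**Power within city.** Paired t test, noncentrality d√n, same true d in every city. The cities are independent, so

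P(cities disagree) = 1 − p₁p₂p₃ − (1−p₁)(1−p₂)(1−p₃).

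At d=0.15: p = 0.227, 0.323, 0.432. All three significant: 0.227 × 0.323 × 0.432 = 0.032. None: 0.773 × 0.677 × 0.568 = 0.297. Disagree: 1 − 0.032 − 0.297 = 0.671.

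| Common effect (SD) | Kansas City | Birmingham | Oakland | Cities disagree |
|---|---|---|---|---|
| 0 | 5% | 5% | 5% | 14% |
| 0.10 | 13% | 17% | 22% | 43% |
| 0.15 | 23% | 32% | 43% | 67% |
| 0.20 | 37% | 52% | 66% | 77% |
| 0.25 | 52% | 71% | 85% | 67% |
| 0.30 | 68% | 85% | 95% | 45% |
| 0.35 | 81% | 94% | 99% | 25% |

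Disagreement exceeds 50% for common effects from about 0.11 to 0.29 SD. It is 70% at the recomputed d=0.158, 71% at g=0.08, 71% at rho=0.16 and 64% at f=0.08. At the 1-month N of 391 (about 83 / 128 / 180) and d=0.15 it is 73%.

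**Direct test on the same data.** In simulation (100,000 runs, common d=0.15), separate tests disagreed in 67% of runs, while a 2-df heterogeneity test declared a difference in 5.2%.

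**Role of unequal sizes.** With three equal cities of 104, disagreement at d=0.15 is 66%, almost the same. Size affects direction. At d=0.15, Oakland significant and Kansas City not: 0.432 × 0.773 = 33%. The reverse: 0.227 × 0.568 = 13%.

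**What a direct comparison can detect.** Pairwise difference with 80% power = 2.802 × √(1/n₁ + 1/n₂): Kansas City–Birmingham 0.44, Kansas City–Oakland 0.41, Birmingham–Oakland 0.36 SD of change.

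**The case against.** The plan does not say that significance will be compared across cities, nor that any city will be declared to have no effect. The analysis is a secondary follow-up step, and city estimates with intervals might well be reported. All of that stands. The supportable statement is that the plan names subsample analysis as the means of identifying site-specific effects and gives no criterion for a difference.

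A reader might infer four stronger things that the documents or the arithmetic do not support.

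- **That the plan will tend to report an effect in Oakland and none in Kansas City.** With a common effect, that pattern has a 33% chance at d=0.15 and never exceeds about 43%.
- **That unequal city sizes are the cause.** Equal cities disagree almost as often; low power within each city is the cause.
- **That disagreement is usual whatever the effect.** It is below 50% for common effects under about 0.11 or above about 0.29 SD.
- **That the module's localised content depends on this analysis.** The Intervention content and modality section draws local knowledge from the Aim 1 interviews; Aim 3 follow-up data come after the module is delivered.

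The quoted sentence follows the HLM step, so site-specific effects may mean predictor–outcome associations rather than change over time. The argument is the same (71% disagreement at rho=0.16), but a remedy confined to site-by-time terms would miss it.

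Finally, 67% and 5% measure different things. Disagreement on significance is not itself a claim that cities differ; it is how often the results would invite one.

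**Conclusion.** The concern holds in this form: the only named route to site-specific effects is separate analysis of three subsamples, and that route cannot show whether effects differ by city. With the same true effect everywhere, the cities disagree on significance in 64% to 71% of trials across the plan's four stated planning effects (67% at d=0.15).

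These figures rest on proportional loss by city, two-sided unadjusted 5% tests, and d read as within-woman change. The three cohorts were recruited in different settings and at different times, so actual city numbers may depart from 67 / 102 / 144. The equal-size result suggests that a moderate departure would change the overall disagreement little, though it would change its direction.

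The pooled Aim 3 analyses are not affected. The change should be made, but it concerns a secondary analysis.

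**What to change.** Replace the subsample sentence in the Data analysis section with a specification along these lines:

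1. In the pooled Aim 3 models, add site-by-time terms to the GCM and site-by-predictor terms to the HLM.
2. Report the joint 2-df site interaction test for each term of interest (with time coded so that the site contrast has 2 df).
3. Give city estimates with confidence intervals from those pooled models, labelled exploratory.
4. State that no site difference will be claimed because significance differs between cities.
5. State that, at the expected numbers, only large pairwise differences (about 0.36 to 0.44 SD of change, under proportional loss) are detectable with 80% power.

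This changes the analysis text only; it needs no new participants or data. The cost is fewer site claims, because the interaction test has modest power. A non-significant interaction must not be read as showing that the cities are alike.
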